# 16.9 Sample Size Justification

The primary endpoint in this study is the Harris Hip Score at minimum 2-year postoperative. It is anticipated that this primary outcome measurement will be obtained on approximately 200 primary THA Subjects due to anticipated attrition. The standard deviation in this outcome will be approximately 10 points (based on historical hip studies). It is therefore anticipated that the margin of error on the mean Harris Hip Score estimate at minimum 2-years postoperatively will be approximately 1.4 points. The study team believes this margin of error is sufficient for this 2-year outcomes and follow-up study. A sample size of N=30 hemi-hip arthroplasty procedures was established as a feasible number.

### 16.10 Analysis Plan

Results for the cohorts of Subjects who were enrolled with a primary THA, and who were enrolled with a primary hemi-hip arthroplasty procedure will be summarized side-by-side, and overall, unless otherwise stated. Demographics, baseline subject characteristics, procedure characteristics and the primary and secondary endpoints will be presented overall (pooled) and by study site. Descriptive statistics for dichotomous/categorical variables will include the number and percentage of subjects. For categorical endpoints, 2-sided 95% confidence intervals around observed percentages will be based on the binomial exact method. Descriptive statistics for continuous variables will include the number of subjects, mean, standard deviation, median, minimum, and maximum. For continuous endpoints, 2-sided 95% confidence intervals around the mean will be computed using the t-distribution.

CONFIDENTIAL Page 41 of 53
Version Date: May 7, 2018

DePuy Synthes / Actis® Total Hip System
Protocol #14014 / Version B

### **16.11** Primary Endpoint

The primary endpoint is the total Harris Hip Score at minimum 2 years after cementless primary total hip arthroplasty (THA) or hemi-hip arthroplasty. This primary endpoint analysis will be conducted on both groups combined (primary THA and primary hemi-hip arthroplasty); however, results will also be analyzed separately for each cohort. Descriptive statistics that include the number, per group, of study hips, mean, standard deviation, median, minimum, and maximum will be presented. A 2-sided 95% confidence interval around the mean will be computed using the t-distribution.

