Number of Sites:	A minimum of 10 study sites will participate. Any one site may not enroll more than 40 Subjects (inclusive combination of both THA and hemi-hip arthroplasty Subjects) after reallocation from low enrollment sites, which will ensure that in a worst-case scenario, a minimum of 4 sites must contribute enrollment to the final sample size to represent variability across surgeons.	
Subject Population:	Subjects at participating sites who meet the inclusion/exclusion criteria for this study.	
Sample Size:	Sites will prospectively enroll a total of 255 Subjects to include a minimum of 225 Primary THA Subjects, and a cohort of a minimum of 30 hemi-hip arthroplasty Subjects.	
	The anticipated duration of this investigation is approximately 3- to 4-years from the time of study initiation given that:	
Study Duration:	• It may take up to 1-year from the time of study initiation to enroll total hip arthroplasty Subjects. It is expected that the hemi-hip arthroplasty cohort may take longer than 1-year to enroll.	
	Each Subject will be followed until they have completed their minimum 2-year follow-up.	
	• The study will be closed when all Subjects have completed minimum 2-year follow-up.	

Table 2 Study Summary		
Title:	Actis® Total Hip System 2-Year Follow-up	

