#### 10.1 Primary Objective

Two-year (2 year) information regarding the performance of the commercially available Actis® Total Hip System in order to obtain and evaluate the clinical outcomes on a series of cementless primary total hip arthroplasty (THA) and hemi-hip arthroplasty using clinical, radiographic and device and procedure related adverse event assessments.

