#### 10.2 Primary Endpoint

Investigate the minimum 2-year postoperative functional performance for the Actis® Total Hip System as measured with the Harris Hip Score at minimum 2 years postoperatively for cementless primary total hip arthroplasty. All analyses including the primary endpoint analysis will be conducted on primary THA subjects and a summary for hemi-hip arthroplasty Subjects will be provided separately.

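### Is the 1.4-point margin for the Harris Hip Score, with its simple t-interval, too narrow because it ignores correlation within sites?

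*Combined protocol and SAP*

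**What the plan says.** Section 16.9 expects about 200 THA subjects with a 2-year Harris Hip Score and a standard deviation near 10, and concludes that the "margin of error on the mean Harris Hip Score estimate at minimum 2-years postoperatively will be approximately 1.4 points". Section 16.11 gives the interval: "A 2-sided 95% confidence interval around the mean will be computed using the t-distribution". Neither section mentions site, an ICC or a clustered variance. Section 16.10 adds that "the primary and secondary endpoints will be presented overall (pooled) and by study site".

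On sites, Table 2 requires at least 10 and sets a cap: "Any one site may not enroll more than 40 Subjects". It says the cap ensures that, at worst, "a minimum of 4 sites must contribute enrollment to the final sample size to represent variability across surgeons".

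On the target of inference, section 10.1 speaks of "clinical outcomes on a series of cementless primary total hip arthroplasty (THA) and hemi-hip arthroplasty". Sections 16.3 and 16.7 state that the study tests no hypotheses and that everything is exploratory.

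**The concern.** Patients at one site share surgeons, technique and the clinicians who score the Harris Hip Score (Table 3), so their scores may be correlated. If they are, a standard error computed as though all 200 subjects were independent is too small for a statement about sites in general. The 1.4-point margin is the only quantitative reason given for the THA sample size, and section 8 makes an adequate margin of error a design aim. In a study without hypotheses, the width of the interval is most of what the primary endpoint delivers. Table 2's reference to variability across surgeons suggests that the wider reading was intended. Its four-site worst case also does not match the cap it is derived from, which makes the handling of sites look careless.

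**Working it through.** **Inputs.** n = 200 evaluable THA subjects and SD = 10 (16.9); two-sided 95% (16.3); cap of 40 per site, at least 10 sites, 255 subjects including 225 THA (Table 2). The documents give no ICC, so 0 to 0.10 is an assumption. Site stands in for surgeon, because the number of surgeons per site is not given.

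**The plan's own figure.** 1.96 × 10/√200 = 1.386. With t on 199 degrees of freedom it is 1.394. Both round to 1.4, so there is no arithmetic error.

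**If sites are treated as a sample from a wider population.** Design effect DE = 1 + (m − 1) × ICC, and margin = 1.96 × 10 × √(DE/200). Here m = 20 for ten equal sites and m = 33.3 for six, the fewest that can hold 225 THA subjects under the cap. Using sites-minus-one degrees of freedom replaces 1.96 by 2.262 (9 df) or 2.571 (5 df).

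| ICC | DE, 10 sites | Margin | Margin, 9 df | DE, 6 sites | Margin | Margin, 5 df |
|---|---|---|---|---|---|---|
| 0 | 1.00 | 1.39 | 1.60 | 1.00 | 1.39 | 1.82 |
| 0.01 | 1.19 | 1.51 | 1.74 | 1.32 | 1.59 | 2.09 |
| 0.02 | 1.38 | 1.63 | 1.88 | 1.65 | 1.78 | 2.33 |
| 0.05 | 1.95 | 1.94 | 2.23 | 2.62 | 2.24 | 2.94 |
| 0.10 | 2.90 | 2.36 | 2.72 | 4.23 | 2.85 | 3.74 |

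**What the planned t-interval covers.** Simulation, 40,000 replicates per setting:

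| ICC | Participating sites, 10 | Participating sites, 6 | Wider population, 10 | Wider population, 6 |
|---|---|---|---|---|
| 0 | 95.2% | 95.0% | 95.0% | 94.9% |
| 0.01 | 95.1% | 95.3% | 92.8% | 91.0% |
| 0.02 | 95.3% | 95.1% | 90.5% | 87.6% |
| 0.05 | 95.5% | 95.6% | 84.1% | 77.5% |
| 0.10 | 95.8% | 95.9% | 75.2% | 66.1% |

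Coverage for the participating sites does not fall because, with the sites fixed, only within-site variation moves the mean. At ICC 0.10 the true standard error is 10 × √(0.90/200) = 0.67, while the plan uses about 10/√200 = 0.71. The interval is then slightly conservative.

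**What a site-robust interval would cost.** Even at ICC 0 it is wider than the planned one by 2.262/1.972 = 1.147 (about 15%) with ten sites and 2.571/1.972 = 1.304 (about 30%) with six. For the participating sites it over-covers, rising from 95.3% at ICC 0 to 99.7% at ICC 0.10 with ten equal sites. For a wider population it covers about 95% with equal sites, but 93.3 to 94.3% in one example of ten unequal sites. Reallocation up to the cap makes unequal sizes likely here.

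**The site floor.** 4 × 40 = 160, short of 255 and of 225. 255/40 = 6.4, so seven sites; 225/40 = 5.6, so six. A four-site floor for 255 subjects would need a cap of 64 (255/4 = 63.75).

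**The case for a change.** The best argument for a change is that the plan itself brings surgeons into the picture. Table 2 justifies the cap by variability across surgeons, yet the primary interval carries no such component, and tables by site display the variation without feeding it into the precision. Even a small correlation matters on that reading: at ICC 0.02 a nominal 95% interval covers about 90% with ten sites. A sensitivity interval needs no new data, since the site number is part of each Subject number (section 9.6).

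Some of this stands. The independence assumption is not stated, and the interval should not be read as covering surgeons at large. But the Table 2 clause explains why enrolment is spread over sites; it does not define what is estimated. Nothing says the sites were sampled from a wider population, and a wider interval would not make chosen sites representative. The six-site figures also need all THA subjects to fall in six of at least ten sites, which the cap permits but nothing suggests happened. Section 16.12 applies the primary method to the 3-month and 1-year scores, and section 16.10 uses independence-based intervals throughout, so changing one interval would either spread or leave the plan uneven.

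**Conclusion.** The margin and the t-interval are correct for the series of patients at the participating sites, which is the target the objective describes. The shortfall needs both a positive ICC, which the documents do not supply, and a claim across surgeons that no objective or analysis section makes. Choosing between fixed and random sites is a fair trade-off, and the alternative has its own cost in width and coverage. No decision depends on the choice: there is no threshold, and section 10.6 dates completion of THA enrolment to June 5, 2017, before Version B of May 7, 2018. If readers want to judge variation between sites, by-site results are already planned, and by-site n, mean and SD for the THA cohort would be enough to compute an ICC and a site-robust interval.

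The four-site statement is a clerical slip in the safe direction. The cap guarantees seven sites for 255 subjects, more than Table 2 claims, and correcting the number would change no enrolment, result or conclusion.

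One separate matter is not settled here. Section 10.2 says "All analyses including the primary endpoint analysis will be conducted on primary THA subjects", while section 16.11 says "This primary endpoint analysis will be conducted on both groups combined". Those sections need reconciling on their own account. The figures above are for THA because the 16.9 margin is for THA.

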# **16.12** Secondary Endpoints

- Harris Hip score at 3 months and 1 year. The same methods as described for the primary endpoint will be utilized for this secondary endpoint.
- Radiographic evaluation at 2 years post-operatively. Radiographs will be read by an independent radiographic reviewer (IRR) at 6 weeks to act as a baseline measurement to be compared to radiographs taken at later time points (3 months, 1 year, and 2 years). Parameters measured include stem subsidence, shell migration, shell inclination angle, osteolytic lesions, radiolucencies, heterotopic ossification, demarcation lines (sclerotic lines), porous coating integrity (delamination/bead shedding), calcar remodeling, femoral stem tilt (appearance), and leg length discrepancy. Please refer to the Radiographic Parameters **Appendix D** for details on how these measurements are taken. For analysis purposes, minimum change from baseline thresholds are defined below for several of these parameters; These threshold levels are considered to be clinically important change from baseline thresholds:
  - o Femoral stem Subsidence greater than 2 mm
  - Acetabular shell Migration greater than 2 mm
  - o Acetabular shell Inclination angle change greater than 4 degrees
  - Osteolysis greater than 5 mm in the greatest dimension
  - o Radiolucencies greater than 2 mm in width

The percentage of cases that exceed the thresholds provided above will be presented by visit for each radiographic parameter, along with the number of cases and 2-sided 95% confidence intervals based on the binomial exact method. A listing of the cases exceeding the thresholds will also be provided along with the corresponding numerical measurement (i.e. radiolucency width measured in mm). Further, the number and percentage of the other radiographic parameters will be presented along with a listing of cases with undesirable results (*i.e.* cases with Heterotopic Ossification not equal to 'None').

• Leg length discrepancy (LLD) will be analyzed by study visit in several ways:

CONFIDENTIAL Page 42 of 53
Version Date: May 7, 2018

DePuy Synthes / Actis® Total Hip System
Protocol #14014 / Version B

- Analysis of "True" versus "Perceived" LLD: Each subject will be asked, yes or no, if they
  Perceive that they have LLD both before and after undergoing hip replacement. Percentages
  will be presented along with 95% binomial exact confidence intervals.
- Radiographic measurements will provide True LLD by measuring each leg to the nearest millimeter. A LLD of 3 cm or greater will be considered a true LLD. A McNemar's test of discordant pairs will be utilized to compare perceived vs. actual LLD before surgery, and also to compare perceived vs. actual LLD after surgery.
- o Analysis of Change (post-surgical pre- surgical) of True LLD: Compare the difference between the absolute true LLD before and after hip replacement surgery for those cases that had a true LLD prior to hip replacement surgery (using a definition of 3 cm or greater as the threshold). The analysis variable will be the absolute value of the difference between the right and left knee and a paired t-test will be used to assess this difference.
- Analysis of proportion of cases that have true LLD after surgery will be presented and this
  will be compared to the proportion that had true LLD prior to surgery; McNemar's test of
  discordant pairs will be conducted.
- The type and frequency of AEs through 2 years post-operatively will be presented in table form and via a listing. Frequencies and listing of AE's seriousness, severity, whether unanticipated, outcome, and treatment will also be presented.
- Device survivorship at 2 years post-operatively. Kaplan-Meier survivorship will be conducted with removal of any component, defined as revision, for any reason specifying the event of interest. Cases not revised will be censored at their date of last follow-up, death, or withdrawal from the study. Survivorship point estimates and 95% confidence intervals will be presented when 40 subjects are left being followed. Survivorship analysis is not planned for the cohort of hemi-hip subjects as the sample size is insufficient; however, a listing will be provided to present all subjects requiring removal of any component.
- Stem Revision at 2 years post-operatively.
- Kaplan-Meier survivorship will be conducted with removal specifically of the femoral stem component, defined as revision, for any reason specifying the event of interest. Cases not revised will be censored at their date of last follow-up, death, or withdrawal from the study. Survivorship point estimates and 95% confidence intervals will be presented when 40 subjects are left being followed. Survivorship analysis is not planned for the cohort of hemi-hip Subjects as the sample size is insufficient; however, a listing will be provided to present all Subjects requiring removal of the femoral stem component.

CONFIDENTIAL Page 43 of 53
Version Date: May 7, 2018

DePuy Synthes / Actis® Total Hip System
Protocol #14014 / Version B

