# 16.3 Levels of Significance

There are no pre-specified hypotheses, and all analyses are exploratory. Confidence intervals and p-values may be provided to facilitate clinical judgement. Unless otherwise stated, p-values will be 2-sided and confidence intervals will be 2-sided 95% confidence intervals with no adjustments for multiplicity.

CONFIDENTIAL Page 39 of 53
Version Date: May 7, 2018

DePuy Synthes / Actis® Total Hip System
Protocol #14014 / Version B

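### The perceived-versus-actual leg-length McNemar test pairs a yes/no perception of no stated size with a 3 cm cut-off, so it can reject when no subject has misperceived anything

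*Combined protocol and SAP*

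**What the plan says.** The leg-length part of Section 16.12 (Secondary Endpoints) sets up a comparison of true with perceived LLD.

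- Perception: "Each subject will be asked, yes or no, if they" "Perceive that they have LLD both before and after undergoing hip replacement". The section attaches no minimum size to the question.
- Measurement: "Radiographic measurements will provide True LLD by measuring each leg to the nearest millimeter".
- Cut-off: "A LLD of 3 cm or greater will be considered a true LLD".
- Test: McNemar's test on discordant pairs is used "to compare perceived vs. actual LLD before surgery, and also to compare perceived vs. actual LLD after surgery".

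The section gives no second cut-off for this comparison and no cross-summary of millimetres by perceived status. Section 16.3 (Levels of Significance) says: "There are no pre-specified hypotheses, and all analyses are exploratory". It also says that "p-values will be 2-sided and confidence intervals will be 2-sided 95% confidence intervals with no adjustments for multiplicity".

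**The concern.** The two paired variables do not share a threshold. One is any discrepancy that the subject notices. The other is a discrepancy of at least 30 mm. A subject with a measured difference of 15 or 25 mm who answers yes is right, yet lands in the cell for perceived but not actual. McNemar's test then compares the share answering yes with the share at or above 30 mm, and some of the gap between them may come from the cut-off alone.

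What is at stake is interpretation. A small p-value in an analysis of true against perceived LLD invites the reading that subjects perceive discrepancies that are not there, when they may be reporting real ones below 3 cm. The plan does not state that reading, but it does nothing to prevent it.

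The point is limited to the cut-off in the perceived-versus-actual test. It does not cover the other analyses that use 3 cm.

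**Working it through.** **Inputs.** Yes/no perception, 3 cm cut-off, 1 mm resolution and McNemar's test: Section 16.12. Two-sided p-values: Section 16.3. About 200 evaluable primary THA subjects and 30 hemi-hip subjects: Section 16.9. No alpha is stated, so 0.05 is assumed from the 95% intervals. The 200 is the expected number with a 2-year Harris Hip Score; no separate count is given for LLD.

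**The plan's own figure.** The only precision figure in Section 16.9 is a margin of about 1.4 points for the Harris Hip Score. It reproduces: 1.96 × 10 / √200 = 1.39. It has no bearing on LLD, for which the plan gives no sample size, power or expected rate.

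**Step 1: cells under accurate perception.** Let b = perceived yes, actual no, and c = perceived no, actual yes. If every subject perceives an LLD exactly when it reaches some limit below 30 mm, then c = 0, and b is the number with an LLD from that limit up to 29 mm. This follows from the definitions and needs no distribution.

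**Step 2: how large b must be.** With c = 0:

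- Exact two-sided p = 2 × 0.5^b. b = 5 gives 0.063; b = 6 gives 0.031.
- Continuity-corrected chi-square = (b − 1)²/b on 1 df. b = 6 gives p = 0.041.
- Uncorrected chi-square = b on 1 df. b = 4 gives p = 0.0455.

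So rejection needs 6 subjects (6/200 = 3%) with the exact or corrected test, or 4 (4/200 = 2%) with the uncorrected test. The plan does not say which version applies.

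**Step 3: rejection probability by share q.** Let q be the share of subjects who correctly report an LLD below 3 cm. Rejection probability is P(B ≥ 6) for the exact test, or P(B ≥ 4) for the uncorrected test, with B ~ Binomial(n, q).

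| n | q | exact | uncorrected |
|---|---|---|---|
| 200 | 1% | 0.02 | 0.14 |
| 200 | 2% | 0.21 | 0.57 |
| 200 | 3% | 0.56 | 0.85 |
| 200 | 5% | 0.94 | 0.99 |
| 200 | 10% | >0.999 | >0.999 |
| 30 | 10% | 0.07 | 0.35 |
| 30 | 20% | 0.57 | 0.88 |
| 30 | 30% | 0.92 | 0.99 |

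**Step 4: what q might be.** The documents give no LLD distribution, so this step is illustration. Assume a right-left difference that is normal with mean 0, an absolute value rounded to 1 mm, and perception that is accurate from a limit t upward. Then q = 2 × [Φ(−(t − 0.5)/SD) − Φ(−29.5/SD)]. For t = 10 and SD = 5, q = 0.057, so 200 × 0.057 gives about 11.5 discordant pairs. Rejection with the exact test, n = 200:

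| Perception limit | SD 5 | SD 6 | SD 8 | SD 10 | SD 12 | SD 15 |
|---|---|---|---|---|---|---|
| 10 mm | 98% | 100% | 100% | 100% | 100% | 100% |
| 15 mm | 0% | 10% | 99.5% | 100% | 100% | 100% |
| 20 mm | 0% | 0% | 7% | 92% | 100% | 100% |

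On the same assumption, the share at or above 30 mm is 0.02% at SD 8, 0.3% at SD 10 and 4.9% at SD 15.

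**Step 5: discordance the other way.** Subjects at or above 30 mm who answer no add to c and can mask the effect. With b = 10 the exact test stops rejecting at c = 3 (p = 0.09); with b = 20, at c = 9 (p = 0.06). A non-significant result therefore does not show agreement either.

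**The case against.** **Exploratory status.** There is no pre-specified hypothesis, p-values are optional aids to clinical judgement, and this is one part of one secondary endpoint, with no effect on the primary endpoint, the sample size or any decision rule. This stands and sets the weight of the point. It does not make the comparison answer its own question.

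**Other output helps.** Section 16.12 already reports perceived percentages with exact intervals and the proportion with true LLD after surgery, and Section 16.10 provides descriptive statistics for continuous variables. This narrows the gap, but nothing planned sets millimetres against perceived status.

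**Unseen wording.** The eCRFs (Appendix A) and radiographic protocol (Appendix D) were not available. A size limit in the question itself cannot be excluded. The mismatch is established for Section 16.12 only.

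**Tempting stronger readings.** A reader might infer that the test rejects whenever perception is accurate, or that most discordant pairs come from the cut-off. Neither is supported. Both depend on an LLD distribution and a perception limit that the documents do not give, and several of the scenarios above give rejection of 0 to 10%. A reader might also argue that the test is useless because it can reject as often with random as with accurate perception. That reflects McNemar's comparison of marginal proportions, which holds at any cut-off. It is a matter of the choice of statistic, not of the 3 cm threshold.

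**Conclusion.** The concern holds in conditional form. As Section 16.12 is written, correctly perceived discrepancies below 3 cm count as discordant, so the perceived-versus-actual test can reject with no misperception at all. The firm result is the threshold: with fully accurate perception, 6 such subjects, or 3% of about 200, suffice for the exact test at an assumed alpha of 0.05. Whether that number is reached cannot be told from the documents. Under the assumed normal model the probability runs from about 0% to about 100%. At a share of about 1% or less among 200 subjects the exact test seldom rejects, and in the 30 hemi-hip subjects a share of roughly 20 to 30% is needed for rejection to be likely.

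Severity is minor: one exploratory comparison is affected, and the primary endpoint is not.

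**What to change.** In Section 16.12, replace the perceived-versus-actual McNemar test with a summary on the millimetre scale already recorded. Before and after surgery, summarise radiographic absolute LLD in mm for subjects who perceive an LLD and for those who do not, and give the difference between the groups with its 95% CI. An ROC area for perceived status against millimetres is optional.

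Within this comparison, keep the 3 cm category as descriptive only. Add a sentence that a perceived yes with a measured LLD below 3 cm is not to be read as a false perception. Check the Appendix A question wording at the same time; if it sets a size, state that size in Section 16.12.

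The cost is SAP wording and minor programming, with no new data, visits or readings. One exploratory p-value is replaced by an estimate with an interval.

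### The only millimetre-scale test of pre- to postoperative leg length change is confined to subjects measured at 3 cm or more before surgery, so regression to the mean pushes it toward improvement

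*Combined protocol and SAP*

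**What the plan says.** Section 10.3 names LLD as part of the radiographic secondary endpoint. Section 16.12 sets the definition: "A LLD of 3 cm or greater will be considered a true LLD", from radiographs with each leg measured to the nearest millimetre. It opens with "Leg length discrepancy (LLD) will be analyzed by study visit in several ways" and then specifies three kinds of test:

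- McNemar tests of perceived against actual LLD, run separately before and after surgery.
- A comparison of absolute LLD before and after surgery "for those cases that had a true LLD prior to hip replacement surgery (using a definition of 3 cm or greater as the threshold"), for which "a paired t-test will be used to assess this difference".
- A McNemar test in which the postoperative proportion with true LLD "will be compared to the proportion that had true LLD prior to surgery".

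For radiographic parameters generally, "Radiographs will be read by an independent radiographic reviewer (IRR) at 6 weeks to act as a baseline measurement", and the five listed change-from-baseline thresholds do not include LLD. For the remaining parameters, "Further, the number and percentage of the other radiographic parameters will be presented along with a listing of cases with undesirable results". Section 16.10 adds, for any continuous variable, "Descriptive statistics for continuous variables will include the number of subjects, mean, standard deviation, median, minimum, and maximum". Sections 10.8 and 16.2 state that there is no control group, and Section 16.3 states that all analyses are exploratory.

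**The concern.** Subjects enter the paired t-test because their preoperative reading was extreme, and change is then measured from that same reading. Some of them reached 30 mm partly through reading or positioning error. On the next film the error is drawn afresh, and the group mean falls even if no leg has changed. Without a control group, a repeat baseline film or an error correction in the analysis text, this fall cannot be separated from a surgical effect.

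The other planned analyses do not fill the gap:

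- The perceived-versus-actual tests work within one time point.
- The pre/post McNemar test has no baseline filter and counts every new discrepancy of 3 cm or more, but it is binary. A subject who goes from 5 to 25 mm is a concordant pair and contributes nothing.
- The 6-week film is already postoperative, so comparisons with it say nothing about change from before surgery.
- By-visit summaries and listings are not paired pre-to-post change.

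Two things are at stake. The one p-value planned for millimetre change comes from the subgroup in which chance favours the device. And a discrepancy that surgery creates or enlarges, but that stays below 3 cm, has no paired estimate, although Section 13 lists lengthening or shortening of the limb among the intra-operative complications.

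**Working it through.** **Inputs.** From the documents: threshold 30 mm; absolute LLD as the analysis variable; two-sided 5% paired t-test; about 200 THA subjects with 2-year data (Section 16.9, stated for the Harris Hip Score and borrowed here for paired films). The plan gives no LLD figure to reproduce.

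Assumed, because the documents give neither: true preoperative LLD, *T*, normal with mean 0 and SD 10, 12, 15 or 20 mm; independent film error with SD *e* = 3 or 5 mm (1 mm as a favourable case); no true change at surgery.

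**Closed form.** Let *s*² = SD² + *e*² be the variance of a reading.

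- Expected number eligible = 200 × 2 × [1 − Φ(30/*s*)].
- Mean preoperative reading of those selected: *m* = *s* × φ(30/*s*) / [1 − Φ(30/*s*)].
- Expected false reduction = *m* × *e*²/*s*², since a fraction *e*²/*s*² of a reading is on average error. Sign reversals are negligible at 30 mm.

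Worked case, SD 15 and *e* = 5: *s*² = 225 + 25 = 250, *s* = 15.81, 30/*s* = 1.897. Eligible = 200 × 0.0578 = 11.6. *m* = 36.1 mm. False reduction = 36.1 × 25/250 = 3.6 mm.

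**Simulation.** Pre = |*T* + e1| and post = |*T* + e2|, selected on pre ≥ 30. Bias is from 10 million draws and rejection rates from 20,000 trials with at least 2 eligible subjects. The simulated bias agrees with the closed form to within 0.03 mm in the rows below (error SD 3 / 5 mm, n = 200).

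| SD of true LLD (mm) | Expected eligible | False mean reduction (mm) | Rejection at nominal 5% | Trials with ≥ 2 eligible |
|---|---|---|---|---|
| 10 | 0.8 / 1.5 | 2.7 / 6.7 | 7% / 14% | 20% / 43% |
| 12 | 3.1 / 4.2 | 2.0 / 5.1 | 10% / 22% | 82% / 93% |
| 15 | 10.0 / 11.6 | 1.4 / 3.6 | 15% / 36% | 100% |
| 20 | 27.6 / 29.1 | 0.9 / 2.3 | 18% / 40% | 100% |

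At SD 15 and 20, at least 98% of rejections were toward improvement.

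**Same data without the filter.** In all subjects the mean change was within 0.003 mm of zero and the t-test rejected 4.8% to 5.3% of the time. The unfiltered pre/post McNemar test (exact) rejected at most 2.7% of the time.

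**Subjects left out.** 200 − 0.8 = 199.2 (SD 10, error 3) down to 200 − 29.1 = 170.9 (SD 20, error 5).

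**Sensitivity.**

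- Error SD 1 mm, normal LLD: bias 0.33, 0.23, 0.16 and 0.10 mm for SD 10, 12, 15 and 20; rejection 6.1% and 6.6% at SD 15 and 20.
- Heavier-tailed (Laplace) LLD, error 3 / 5: bias 0.85 / 2.36 mm at SD 15 and 0.63 / 1.76 mm at SD 20; rejection 10.0% / 19.8% and 10.9% / 22.7%.
- n = 225 (the planned THA minimum): rejection 16.9% / 40.9% at SD 15 and 19.6% / 44.5% at SD 20.
- Readings rounded to 1 mm, in a separate 4-million-subject simulation: bias at SD 15 again 1.4 / 3.6 mm.
- Error SD 0: no bias.

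**The case against.** Several points on the other side are fair.

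- **Little depends on this p-value.** Section 16.3 makes everything exploratory, Section 16.7 disclaims hypotheses, and no success criterion is attached to LLD. This stands and limits the severity. It does not justify a calculation that leans one way: Section 16.3 offers p-values as an aid to clinical judgement.
- **The bias may be small beside a real correction.** At SD 15 to 20 the selected group averages about 36 to 39 mm before surgery, so a bias of 0.9 to 3.6 mm is about 2% to 10% of baseline, and under 0.5% at error SD 1 mm. This stands for the size of the bias. It supplies no estimate for subjects below 3 cm.
- **The largest biases occur where the test hardly runs.** Correct: the 2.7 and 6.7 mm figures belong to settings with about 1 eligible subject. The plan then has either almost nobody to test or a biased test.
- **The size rests on unseen inputs.** Appendix D, which holds the measurement method, was not available, and a mixture of indications may fit better than one normal distribution. With an assumed 90% at SD 8 and 10% at SD 30, the bias is 0.06, 0.5 and 1.5 mm for error SD 1, 3 and 5. This stands for the size. The direction does not change.
- **By-visit means would show an unselected shift.** Possibly, if Section 16.10 is applied to LLD. Those are separate summaries at each visit, not a paired change with its own interval. Section 16.13 writes out change from preoperative scores for FJS-12 and HOOS; Section 16.12 does not do so for LLD.
- **Correction among discrepant patients is a legitimate question.** It is, and an all-subject mean will dilute it. For that reason the subgroup should be kept as a labelled description.

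**Conclusion.** The concern holds. The only specified pre-to-post test in millimetres selects on its own baseline with no control, so any non-zero reading error biases it toward improvement. That direction does not depend on the assumed distribution. The size does: 0.9 to 3.6 mm with rejection rates of 15% to 40% under a normal LLD with SD 15 to 20 mm and error SD 3 to 5 mm; 0.6 to 2.4 mm and 10% to 23% under the heavier-tailed alternative; and 0.1 to 0.3 mm with near-nominal error if films repeat to within an SD of 1 mm. In every n = 200 setting tabulated, at least 170 subjects have no specified paired millimetre estimate. Because LLD is one part of a secondary endpoint in an exploratory study, this should be corrected but does not threaten the study's main result.

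**What to change.** In Section 16.12, remove the preoperative 3 cm condition from the change analysis. Analyse post-minus-pre change in absolute radiographic LLD (mm) in all subjects with paired films, by visit including 2 years, giving n, mean change, 95% confidence interval and the number whose absolute LLD increased. Keep the pre/post McNemar test as it is. Report the subgroup at 3 cm or more before surgery descriptively, without a p-value, and label it as subject to regression to the mean.

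The cost is SAP wording and one more table. The Section 6 schedule already has AP pelvis films for LLD before surgery and at every follow-up visit, and Section 16.12 already measures each leg to the nearest millimetre. Precision would be adequate: with 200 pairs the half-width is t(0.975, 199) × SD/√200 = 1.972 × SD/14.14, which is 0.7, 1.4 or 2.1 mm for an assumed SD of change of 5, 10 or 15 mm.
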